8.3.1. Time Period and Frequency for Collecting AE and SAE Information

- All SAEs will be collected from the signing of the ICF until the end of the study at the time points specified in the SoA (Section 1.3).
- All AEs will be collected from the start of intervention until the end of the study at the time points specified in the SoA (Section 1.3).
- Medical occurrences that begin before the start of study intervention but after obtaining informed consent will be recorded as Medical History/Current Medical Conditions not as AEs.

- All SAEs will be recorded and reported to the sponsor or designee immediately and under no circumstance should this exceed 24 hours, as indicated in Appendix 3. The investigator will submit any updated SAE data to the sponsor within 24 hours of it being available.
- Investigators are not obligated to actively seek information on AEs or SAEs after the conclusion of the study participation. However, if the investigator learns of any SAE, including a death, at any time after a participant has been discharged from the study, and he or she considers the event to be reasonably related to the study intervention or study participation, the investigator must promptly notify the sponsor.

8.3.2. Method of Detecting AEs and SAEs

Care will be taken not to introduce bias when detecting AE and/or SAE. Open-ended and non-leading verbal questioning of the participant is the preferred method to inquire about AE occurrence.

8.3.3. Follow-up of AEs and SAEs

After the initial AE/SAE report, the investigator is required to proactively follow each participant at subsequent visits/contacts. All SAEs and non-serious AEs of special interest (as defined in Section 8.3.6)], will be followed until the event is resolved, stabilized, otherwise explained, or the participant is lost to follow-up (as defined in Section 7.3). Further information on follow-up procedures is given in Appendix 3.

8.3.4. Regulatory Reporting Requirements for SAEs

- Prompt notification by the investigator to the sponsor of an SAE is essential so that legal obligations and ethical responsibilities towards the safety of participants and the safety of a study intervention under clinical investigation are met.
- The sponsor has a legal responsibility to notify both the local regulatory authority and other regulatory agencies about the safety of a study intervention under clinical investigation. The sponsor will comply with country-specific regulatory requirements relating to safety reporting to the regulatory authority, IRB/IEC, and investigators.
- Investigator safety reports must be prepared for suspected unexpected serious adverse reactions according to local regulatory requirements and sponsor policy and forwarded to investigators as necessary.
- An investigator who receives an investigator safety report describing an SAE or other specific safety information (e.g., summary or listing of SAEs) from the sponsor will review and then file it along with the CIB and will notify the IRB/IEC, if appropriate according to local requirements.

8.3.5. Pregnancy

- Details of all pregnancies in female participants and, if indicated, female partners of male participants will be collected after the start of study intervention and through the end of pregnancy.

- If a pregnancy is reported, the investigator will record pregnancy information on the appropriate form and submit it to VH/GSK within 24 hours of learning of the female participant or female partner of male participant (after obtaining the necessary signed informed consent from the female partner) pregnancy. While pregnancy itself is not considered to be an AE or SAE, any pregnancy complication or elective termination of a pregnancy for medical reasons will be reported as an AE or SAE.
- Abnormal pregnancy outcomes (e.g., spontaneous abortion, fetal death, stillbirth, congenital anomalies, ectopic pregnancy) are considered SAEs and will be reported as such.
- The participant/pregnant female partner will be followed to determine the outcome of the pregnancy. The investigator will collect follow-up information on the participant/pregnant female partner and the neonate and the information will be forwarded to the sponsor.
- Any post-study pregnancy-related SAE considered reasonably related to the study intervention by the investigator will be reported to the sponsor as described in Section 8.3.4. While the investigator is not obligated to actively seek this information in former study participants/pregnant female partner, he or she may learn of an SAE through spontaneous reporting.
- Any female participant who becomes pregnant while participating in the study will discontinue study intervention or be withdrawn from the study.

8.3.6. Adverse Events of Special Interest

Adverse events of special interest include all AEs classified in the cardiovascular (per the Medical Dictionary for Regulatory Activities) system organ class, seizure, and syncope. Additional AEs of special interest within other system organ classes (e.g., GI, neurologic, or psychiatric and skin disorders) may be defined in the reporting and analysis plan.

8.4. Pharmacokinetics

- Whole blood samples of approximately 4 mL will be collected for measurement of plasma concentrations of GSK3640254 and DTG as specified in the SoA (Section 1.3).
- A maximum of 10 samples may be collected at additional time points during the study if warranted and agreed upon between the investigator and the sponsor.
- Instructions for the collection and handling of biological samples will be provided by the sponsor. The actual date and time (24-hour clock time) of each sample will be recorded.
- Samples will be used to evaluate the PK of GSK3640254 and DTG. Samples collected for analyses of plasma concentration may also be used to evaluate safety or efficacy aspects related to concerns arising during or after the study.

8.5. Genetics

Genetics are not evaluated in this study.

8.6. Biomarkers

Biomarkers are not evaluated in this study.

8.7. Immunogenicity Assessments

Immunogenicity is not evaluated in the study.

8.8. Medical Resource Utilization and Health Economics

Medical resource utilization and health economics parameters are not evaluated in this study.

9. STATISTICAL CONSIDERATIONS

9.1. Statistical Hypotheses

There is no formal hypothesis that will be statistically tested in this study.

9.2. Sample Size Determination

As there is no formal research hypothesis being statistically tested in this study, the sample size was not selected based on statistical considerations but determined using feasibility. For each part, approximately 18 participants will be enrolled to ensure that 14 evaluable participants complete the study. If participants prematurely discontinue the study, additional participants may be enrolled after consultation with the sponsor to ensure that the required number of evaluable participants complete the study.

Note: "Enrolled" means a participant's, or their legally acceptable representative's, agreement has been obtained to participate in a clinical study following completion of the informed consent process and screening. Potential participants who are screened for the purpose of determining eligibility for the study, but do not participate in the study, are not considered enrolled, unless otherwise specified by the protocol.

9.2.1. Sample Size Assumptions

Based on the results from a previous study ING113674 the intersubject coefficient of variation (CVb) for DTG was 27-34% and 30-35%, respectively, for AUC(0-∞) and Cmax in the fasted state and 31-35% and 19-24%, respectively in the fed state. Based on the results from a previous study 213567 the intersubject coefficient of variation (CVb) for GSK3640254 was 40.3% and 45.3%, respectively, for AUC(0-τ) and Cmax in the fasted state, and 42.2% and 35.6%, respectively in the fed state.

It was assumed that intrasubject coefficient of variation (CVw) was approximately 60% of the calculated CVb. Thus, it was decided that a conservative CVw estimate of 21% would be used for the sample size calculation for DTG and 27.2% would be a conservative estimate to use for the sample size calculation of GSK3640254.

Since it was expected that coadministration of GSK3640254 and DTG would increase the exposure of DTG, a range for point estimate for a ratio of 1.0, 1.1, and 1.2 were explored. It was expected that coadministration of GSK3640254 with DTG would have no significant impact on the exposure of GSK3640254, thus a range for point estimate for a ratio of 0.9, 1.0, and 1.1 were explored.

For DTG, with a sample size of 14, 16 and 18 evaluable participants, it was estimated that the precision (i.e., half-width of the 90% confidence interval [CI] on the log and ratio scale) and CI on the original scale for each point estimate would be as follows:

| N | Drug | CVw (%) | Half-Width (log scale) | Half-Width (original scale) | Point Estimate | 90% CI |
|----|------|---------|------------------------|-----------------------------|----------------|--------------|
| 14 | DTG | 21 | 0.139 | 0.149 | 1.0 | (0.87, 1.15) |
| | | | | | 1.1 | (0.96, 1.26) |
| | | | | | 1.2 | (1.04, 1.38) |
| 16 | DTG | 21 | 0.128 | 0.137 | 1.0 | (0.88, 1.14) |
| | | | | | 1.1 | (0.97, 1.25) |
| | | | | | 1.2 | (1.06, 1.36) |
| 18 | DTG | 21 | 0.120 | 0.127 | 1.0 | (0.89, 1.13) |
| | | | | | 1.1 | (0.98, 1.24) |
| | | | | | 1.2 | (1.06, 1.35) |

For GSK3640254, with a sample size of 14, 16 and 18 evaluable participants, it was estimated that the precision (i.e., half-width of the 90% CI on the log and ratio scale) and CI on the original scale for each point estimate would be as follows:

| N | Drug | CVw (%) | Half-Width (log scale) | Half-Width (original scale) | Point Estimate | 90% CI |
|----|------------|---------|------------------------|-----------------------------|----------------|--------------|
| 14 | GSK3640254 | 27.2 | 0.179 | 0.196 | 0.9 | (0.75, 1.08) |
| | | | | | 1.0 | (0.84, 1.20) |
| | | | | | 1.1 | (0.92, 1.32) |
| 16 | GSK3640254 | 27.2 | 0.166 | 0.181 | 0.9 | (0.76, 1.06) |
| | | | | | 1.0 | (0.85, 1.18) |
| | | | | | 1.1 | (0.93, 1.30) |
| 18 | GSK3640254 | 27.2 | 0.155 | 0.168 | 0.9 | (0.77, 1.05) |
| | | | | | 1.0 | (0.86, 1.17) |
| | | | | | 1.1 | (0.94, 1.28) |

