4. STUDY DESIGN

4.1. Overall Design

This is a Phase 1, 2-part, randomized, open-label, single-dose, crossover study in healthy participants to compare the relative BA of 2 FDCs of GSK3640254 /DTG , 150 mg/50 mg with GSK3640254 / DTG, 150 mg/ 50 mg administered together as single agents (Part 1) and to assess the effect of food on the PK of the selected FDC of GSK3640254 / DTG from Part 1 (Part 2). Participants in both Part 1 and Part 2 will be screened within 35 days before the first dose of study intervention.

Part 1 will consist of a screening period and 3 treatment periods with a single dose of study intervention per treatment period.

Part 2 will consist of a screening period and 2 treatment periods with a single dose of study intervention per treatment period. This will be followed by an End of Study analysis.

Participants will be randomly assigned to receive treatment sequence ABC, BCA or CAB in 1:1:1 ratio in Part 1 and treatment sequence DE or ED in 1:1 ratio in Part 2.

Participants will receive each of the following treatments administered as 1 treatment per period:

Part 1 (Treatment Sequence ABC, BCA, or CAB):

- Treatment A: A single oral dose of GSK3640254 25 mg (2 x tablets), GSK3640254 100 mg (1 x tablet), and DTG 50 mg (1 x tablet) administered together under moderate fat and calorie conditions (reference)
- Treatment B: A single oral dose of GSK3640254 / DTG, 150 mg / 50 mg (1 x monolayer tablet) FDC administered under moderate fat and calorie conditions
- Treatment C: A single oral dose of GSK3640254 / DTG, 150 mg / 50 mg (1 x bilayer tablet) FDC administered under moderate fat and calorie conditions

Treatments A, B, and C will be administered in the fed state. Participants will fast overnight for at least 10 hours prior to breakfast and will receive a moderate fat and calorie meal 30 minutes prior to dosing (Section 5.3.1). Participants will eat this meal in 25 minutes or less. Dose administration will occur within 5 minutes of completion of meal consumption. Participants will not receive any further food until 4 hours after dosing.

Part 2 (Treatment Sequence DE or ED):

- Treatment D: A single oral dose of selected FDC from Part 1 of GSK3640254 / DTG, 150 mg / 50 mg administered under high fat and calorie conditions
- Treatment E: A single oral dose of selected FDC from Part 1 of GSK3640254 / DTG, 150 mg / 50 mg administered under fasted conditions

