The US FDA-approved dose of DTG for treatment naive HIV-infected adult and pediatric patients 12 years and older (and \geq 40 kilogram) is 50 mg once daily. Dolutegravir has low to moderate interparticipant PK variability, a predictable exposure-response relationship, and a 14-hour plasma T_{1/2}. Although coadministration of DTG with low-, moderate-, and high-fat and calorie meals in Study ING113674 [GSK Document Number 2010N105142_00] increased DTG exposures (AUC[0- ∞]) by 33%, 41%, and 66%, respectively, the TIVICAY® product label states that the approved dose regimen is 50 mg once daily taken with or without food based on efficacy and safety results of Phase 3 studies where DTG was taken without regard to meal times. Furthermore, coadministration of DTG (50 mg) and GSK3640254 (200 mg) resulted in no clinically meaningful difference in the steady-state systemic exposure of DTG compared to DTG administered alone with geometric least squares mean ratios of 1.17, 1.09, and 1.24 for AUC(0- τ), Cmax, and C τ , respectively [GSK Document Number 2019N399318_00]. Dolutegravir is available as the single entity product TIVICAY and as a component of other FDCs.

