2.5. Sample Size

As there is no formal research hypothesis being statistically tested in this study, the sample size was not selected based on statistical considerations but determined using feasibility. For each part, approximately 18 participants will be enrolled to ensure that 14 evaluable participants complete the study. If participants prematurely discontinue the study, additional participants may be enrolled after consultation with the sponsor to ensure that the required number of evaluable participants complete the study.

Since it was expected that coadministration of GSK3640254 and DTG would increase the exposure of DTG, ranges for point estimate for a ratio of 1.0, 1.1, and 1.2 were explored. It was expected that coadministration of GSK3640254 with DTG would have no significant impact on the exposure of GSK3640254, thus ranges for point estimate for a ratio of 0.9, 1.0, and 1.1 were explored. The details of the results of these analyses can be found in the protocol Section 9.2.

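### Do the planning ratios in Protocol 9.2.1 need replacing because they rest on a drug-interaction argument and stop at 1.2, below the food effect cited for DTG?

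*Protocol*

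**What the plan says.** Protocol 9.2.1 introduces the DTG planning ratios with "Since it was expected that coadministration of GSK3640254 and DTG would increase the exposure of DTG" and takes 1.0, 1.1 and 1.2. For GSK3640254 it expects no significant effect of coadministration and takes 0.9, 1.0 and 1.1. SAP 2.5 repeats both statements; for DTG, "ranges for point estimate for a ratio of 1.0, 1.1, and 1.2 were explored". The sensitivity table in Protocol 9.2.2 uses 0.9 to 1.2 for either drug at within-participant CVs of 30% and 35%.

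The contrasts are in Protocol 9.4.1 and SAP 7.1.4.1: B versus A and C versus A in Part 1, D versus E in Part 2. Treatment A is the two drugs as single agents "administered together under moderate fat and calorie conditions (reference"; B and C are combination tablets. D and E are the same combination tablet, after a high-fat meal and fasted.

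Protocol 4.3 reports that low-, moderate- and high-fat meals raised DTG AUC(0-∞) "by 33%, 41%, and 66%, respectively".

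On the role of the tables, Protocol 9.1 says "There is no formal hypothesis that will be statistically tested in this study", and Protocol 9.2 says "the sample size was not selected based on statistical considerations but determined using feasibility". The size is then fixed: "For each part, approximately 18 participants will be enrolled to ensure that 14 evaluable participants complete the study". Precision is defined as the "half-width of the 90% confidence interval [CI] on the log and ratio scale".

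**The concern.** An argument about coadministration concerns two drugs together against one drug alone. The earlier interaction study cited in Protocol 4.3 made that comparison, with DTG ratios of 1.17 for AUC(0-τ) and 1.09 for Cmax. This trial has no single-drug arm. In Part 1 any interaction sits in both numerator and denominator of B/A and C/A. In Part 2 only the meal differs. The stated reason therefore fits neither part.

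The range then looks too narrow. If the 66% rise carries over, the D/E ratio for DTG AUC(0-∞) would be near 1.66, and even the widest tabulated DTG interval (0.96 to 1.51, at 14 participants and a CV of 35%) does not contain it. At the planned CV of 21%, no DTG ratio below 1 appears, although a new tablet can lower exposure as well as raise it. These tables are the plan's only account of what 14 to 18 participants can deliver. A reader could conclude that the precision for Part 2 was never worked out.

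**Working it through.** **Inputs.** Within-participant CV of 21% for DTG and 27.2% for GSK3640254 (Protocol 9.2.1), and 30% and 35% (Protocol 9.2.2). N = 14, 16 and 18 evaluable. Two-sided 90% interval. Ratio 1.66 for DTG AUC(0-∞), from the 66% in Protocol 4.3.

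**Step 1: reproduce the tables.** The log-scale standard deviation is σ = sqrt(ln(1 + CV²)), and the half-width is h = t(0.95, N−1) × σ × sqrt(2/N).

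- For CV 21%, σ = sqrt(ln 1.0441) = 0.2077.
- At N = 14, h = 1.771 × 0.2077 × 0.378 = 0.139.

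| CV | Source | N = 14 | N = 16 | N = 18 |
|---|---|---|---|---|
| 21% | computed | 0.1390 | 0.1288 | 0.1205 |
| 21% | stated | 0.139 | 0.128 | 0.120 |
| 27.2% | computed | 0.1788 | 0.1656 | 0.1549 |
| 27.2% | stated | 0.179 | 0.166 | 0.155 |

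The 30% and 35% rows agree as well. All twelve log half-widths are within 0.001 of the stated values, so the differences are last-digit rounding.

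**Step 2: what the ratio does.** The ratio does not appear in h. It enters only afterwards, as R/exp(h) to R × exp(h). The original-scale column is exp(h) − 1, so 1 plus that column is the multiplying factor for any ratio. The plan's own rows confirm this: at N = 14 and CV 21%, 1.2/1.149 = 1.04 and 1.2 × 1.149 = 1.38, as printed.

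**Step 3: the missing rows, from the stated column.** DTG at R = 1.66:

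| CV | N | Factor | 90% CI |
|---|---|---|---|
| 21% | 14 | 1.149 | 1.44 to 1.91 |
| 21% | 18 | 1.127 | 1.47 to 1.87 |
| 30% | 14 | 1.217 | 1.36 to 2.02 |
| 35% | 14 | 1.256 | 1.32 to 2.08 |

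A ratio below 1 is as easy: 0.9/1.149 to 0.9 × 1.149 gives 0.78 to 1.03 at CV 21% and N = 14.

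**Step 4: is precision worse at 1.66?** The width divided by the ratio is 1.149 − 1/1.149 = 0.279, whatever the ratio. The widths are 0.279 × 1.2 = 0.33 and 0.279 × 1.66 = 0.46. The second is larger only because its centre is larger.

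**Step 5: degrees of freedom.** A two-sequence, two-period analysis of Part 2 has N − 2 residual degrees of freedom. At N = 14 and CV 21% this moves h from 0.139 to 0.140, and the interval at 1.66 is still 1.44 to 1.91.

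**The case for a change.** The best argument for a change is that the edit costs almost nothing and the present text is wrong as reasoning. The sentence stands in both documents and fits no contrast. The food-effect comparison is a primary one, and the sponsor had a food-effect figure to hand, yet illustrated ratios near 1. A hurried reader might also add the 0.149 to 1.66 and get an upper limit of 1.81 in place of 1.91.

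The first part stands: the rationale belongs to an interaction study. The rest carries less weight.

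- The additive misreading is contradicted by the table, since 1.2 + 0.149 = 1.35 while the printed limit is 1.38.
- DTG ratios below 1 are not absent. Protocol 9.2.2 tabulates 0.9 for either drug at CVs of 30% and 35%, which are harsher than the planned 21%.
- For Part 1, a range around 1 is a usable choice for a formulation comparison, whatever reason is given for it.
- The 1.66 is a guide and not a firm prediction. It comes from an earlier study of DTG tablets, covers AUC(0-∞) only, and its fasted comparator is implied. The 1.33 and 1.41 concern meals that Part 2 does not use.
- The documents give no food ratio for GSK3640254, so such a row would rest on an assumption. The stated factor of 1.196 at N = 14 already serves whatever ratio is assumed.

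**Conclusion.** No change to the plan follows. The coadministration sentence is a misplaced rationale, and the rows are illustrations around 1. The sample size of about 18 enrolled and 14 evaluable per part came from feasibility, with no hypothesis, margin or power attached. No analysis or selection rule in either document refers to these ratios. Replacing them would leave every half-width, the mixed models, the three contrasts and the reported 90% intervals as they are.

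The tables already describe Part 2 precision: a DTG ratio can be estimated to within a factor of about 1.15 at 14 participants and 1.13 at 18, at a CV of 21%. At 1.66 that means 1.44 to 1.91 and 1.47 to 1.87. Even at a CV of 35% and 14 participants, the interval of 1.32 to 2.08 would lie clear of 1.

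This rests on the stated CVs holding for the D versus E contrast (with 30% and 35% as the tabulated fallback), on 14 to 18 participants contributing both periods, and on 1.66 as an assumed ratio borrowed from the earlier tablet study. If the true ratio differs, the centre of the interval moves and its relative width does not.

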9.2.2. Sample Size Sensitivity

For a sensitivity analysis, assuming a range of within-participant variability, a sample size of 14, 16 and 18 evaluable participants, it was estimated that the precision (i.e., half-width of the 90% CI on the log and ratio scale) and CI on the original scale for each point estimate would be as follows:

| N | Drug | CVw (%) | Half-Width (log scale) | Half-Width (original scale) | Point Estimate | 90% CI |
|----|----------------------------|---------|------------------------|-----------------------------|----------------|--------------|
| 14 | Dolutegravir or GSK3640254 | 30 | 0.196 | 0.217 | 0.9 | (0.74, 1.09) |
| | | | | | 1.0 | (0.82, 1.22) |
| | | | | | 1.1 | (0.90, 1.34) |
| | | | | | 1.2 | (0.99, 1.46) |
| | | 35 | 0.228 | 0.256 | 0.9 | (0.72, 1.13) |
| | | | | | 1.0 | (0.80, 1.26) |
| | | | | | 1.1 | (0.88, 1.38) |
| | | | | | 1.2 | (0.96, 1.51) |
| 16 | Dolutegravir or GSK3640254 | 30 | 0.182 | 0.200 | 0.9 | (0.75, 1.08) |
| | | | | | 1.0 | (0.83, 1.20) |
| | | | | | 1.1 | (0.92, 1.32) |
| | | | | | 1.2 | (1.00, 1.44) |
| | | 35 | 0.211 | 0.235 | 0.9 | (0.73, 1.11) |
| | | | | | 1.0 | (0.81, 1.23) |
| | | | | | 1.1 | (0.89, 1.36) |
| | | | | | 1.2 | (0.97, 1.48) |
| 18 | Dolutegravir or GSK3640254 | 30 | 0.170 | 0.185 | 0.9 | (0.76, 1.07) |
| | | | | | 1.0 | (0.84, 1.19) |
| | | | | | 1.1 | (0.93, 1.30) |
| | | | | | 1.2 | (1.01, 1.42) |
| | | 35 | 0.197 | 0.218 | 0.9 | (0.74, 1.10) |
| | | | | | 1.0 | (0.82, 1.22) |
| | | | | | 1.1 | (0.90, 1.34) |
| | | | | | 1.2 | (0.99, 1.46) |

Approximately 18 participants were planned to be treated to ensure that 14 evaluable participants completed the study.

9.3. Analysis Sets

For the purposes of analysis, the following analysis sets are defined:

| Population | Description |
|-------------------------------|--|
| Screened | All participants who sign the ICF. |
| Randomized | All participants who are randomly assigned to a treatment sequence. |
| Safety | All participants who receive at least 1 dose of study intervention. This population will be used for all demographic and safety summaries. |
| Pharmacokinetic Concentration | The PK Concentration Population will include all participants who undergo plasma PK sampling and have evaluable PK assay results. This population will be used for the PK concentration listings, summary tables, and plotting of concentration/time data. |
| Pharmacokinetic Parameter | The PK Parameter Population will include all participants who undergo plasma PK sampling and have evaluable PK parameters estimated. This population will be used for PK parameter listings, PK parameter summary tables, statistical analysis tables. |

